#### **4.7. Test Reproducibility**

Test reproducibility will not be evaluated on this pilot MRMC study.

#### **4.8. Interim Analyses**

No interim analyses of study endpoints are planned.

#### **4.9. Safety Monitoring Analyses (Adverse Events)**

No adverse events are anticipated on this pilot MRMC study using retrospective cases for which medical management has already been planned and carried out. Readers also are unlikely to report any adverse events. Any adverse events that are reported to BCL will be described.

#### **4.10. Sample Size Calculations (Obtaining Parameters)**

Parameters to use in sample size calculations for the pivotal study will be obtained from analysis of AUCs. The magnitude and direction of differences between AUCs the DBT plus S-View read compared with the FFDM read, and variance components and correlations that influence sample sizes for the pivotal reader study comparing them, will be obtained from MRMC analysis. In particular, we will obtain estimates of average AUC within each modality,

$\sigma^2_b$ ,  $\sigma^2_{ab}$ ,  $r_1$ ,  $r_2$ ,  $r_3$  (all defined below), and  $r_b$ , the correlation between the set of AUCs in the two (2) modalities.

Modeling Framework: Let  $A_{ij}$  be an estimate of the AUC in modality  $i$  ( $i = 1$  for FFDM, 2 for DBT plus S-View) for the  $j^{\text{th}}$  radiologist ( $j = \text{reader 1, ..., } J$  for  $J = 6$ ). We consider the effects of radiologists to be random, because interest extends beyond the radiologists on this study to a larger population of potential radiologists from which these radiologists are a sample.

Obuchowski and Rockette model these estimates using mixed effects ANOVA, as

$$A_{ij} = \mu + \alpha_i + b_j + (ab)_{ij} + e_{ij}$$

where

- $\mu$  is the overall AUC across the populations of readers and cases,
- $\alpha_i$  is the fixed effect of modality,
- $b_j$  is a random effect for reader with expectation 0 and variance  $\sigma^2_b$  with random effects for different readers independent of each other,
- $(ab)_{ij}$  is a random effect for the interaction of modality and reader with expectation 0 and variance  $\sigma^2_{ab}$  also with random effects for different readers independent of each other, and
- $e_{ij}$  is random error with expectation 0, variance  $\sigma^2_c + \sigma^2_w$ , and covariance
  - $r_1 \sigma^2_c$  for two AUCs from the same reader in different modalities,
  - $r_2 \sigma^2_c$  for two AUCs from different readers in the same modality, and
  - $r_3 \sigma^2_c$  for two AUCs from different readers in different modalities.

The variance components  $\sigma^2_c$  and  $\sigma^2_w$  are case sample variance and within-reader variance, respectively.

- The random effects  $b_j$ ,  $(ab)_{ij}$ , and  $e_{ij}$  are independent of each other.
- When the readers review the case sample only once in each modality  $(ab)_{ij}$  and  $e_{ij}$  are not identifiable, and we cannot separate  $\sigma^2_{ab}$  from  $\sigma^2_c + \sigma^2_w$ .

Sample Size Estimation Framework: Power and required sample size to achieve it depend on the magnitude and direction of the difference in average AUC between DBT plus S-View and FFDM,  $\hat{A}_2 - \hat{A}_1$ , which we will estimate from this pilot study. Power also depends on the

number of cancer cases, number of non-cancer (benign, recalled, and normal) cases, and number of readers,  $J$ , through the variance of the difference:

$$\text{var}(\hat{A}_2 - \hat{A}_1) = \frac{2}{J} \{ \sigma_{ab}^2 + \sigma_w^2 + \sigma_c^2 [1 - r_1 + (J - 1)(r_2 - r_3)] \}.$$

Numbers of cancer and non-cancer cases enter this variance through  $\sigma_c^2$  from a binormal approximation. The closed-form expression for  $\sigma_c^2$  facilitates use when the ratio of non-cancer cases to cancer cases in the study being planned may differ from that ratio in the pilot study from which estimates of other parameters are obtained. We will use data from this pilot study to estimate the variance components and correlations in  $\text{var}(\hat{A}_2 - \hat{A}_1)$ . To be conservative, the component  $\sigma_{ab}^2$  will be estimated as  $\sigma_b^2 \times (1 - r_b)$  when the unbiased estimate from ANOVA is negative.

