## **1. Introduction**

This document provides the statistical analysis plan (SAP) for FUJIFILM Medical Systems U.S.A., Inc. (Fujifilm) pilot study protocol FMSU2017-002A, which is a retrospective, multi-reader, multi-case (MRMC) pilot study to be conducted with an enriched sample of approximately 100 cases and six (6) board-certified radiologists with a range of experience who will be trained to read and evaluate Fujifilm digital breast tomosynthesis (DBT) and synthesized view (S-View) 2D images. Each radiologist will review full field digital mammography (FFDM) and DBT plus S-View images for each case in a counterbalanced design with an approximately four (4) week memory washout period. The purpose of the pilot reader study is to provide credible performance estimate information in order to properly plan, design, and power the pivotal study. The results of this pilot study may be used to provide supplemental data for an FDA submission; they are not intended to serve as a basis for FDA approval.

This SAP is based on protocol FMSU2017-002A Final Version 1.0 dated 12 October 2017. If the protocol is amended in a manner that requires this SAP to be revised, Fujifilm and Biostatistics Consulting, LLC (BCL) will finalize the revised SAP before locking the database for the primary analysis. If there is a conflict between the protocol and this SAP, the language in this SAP as approved by BCL, Fujifilm, and the study Principal Investigator shall prevail.

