#### **Exclusion Criteria**

- Subjects who are in violation of protocol FMSU2013-004A.
- Subjects who meet exclusion criteria under Fujifilm protocol FMSU2013-004A.
- Subjects with unknown clinical status.
- Any subject whose positive mammogram was not read during the truthing process will not be considered for the pilot reader study.

Case selection. Cases selected for this study were, to the extent possible, those that BCL selected per approved case selection specifications for Fujifilm protocols FMSU2013-004E “A Multi-Reader Multi-Case Controlled Clinical Trial to Evaluate the Comparative Accuracy of the Fujifilm FFDM Plus DBT Versus FFDM Alone in the Detection of Breast Cancer – A Pilot Study” and FMSU2013-004F “A Multi-Reader Multi-Case Controlled Clinical Trial to Assess the Adequacy of Fujifilm FFDM and DBT Reader Training Program – A Pilot Study.” Starting with this case list, Fujifilm replaced cases that were lost to follow-up or otherwise not available to arrive at a final case list for this pilot study FMSU2017-002A.

Demographic and clinical characteristics. Demographic and clinical characteristics were obtained on Fujifilm protocol FMSU2013-004A (see **Appendix 1** for relevant form pages). The sample includes 18 cancer cases and 82 non-cancer cases comprised of 17 benign cases, 19 recall cases, and 46 normal cases. Cases without biopsy are from the screening pathway and have one-year negative imaging follow-up.

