## **4. Statistical Methods**

Informed consent. By approving this SAP, Fujifilm confirms the following: All subjects whose images were acquired under FMSU2013-004A and selected for this study were consented.

As part of the consent process, subjects agreed that image data and supporting documentation could be used for future research and investigations. Each reader will be consented before initiating the reader study.

Masking to protect identities. Study case identification numbers and study reader numbers will be assigned to all cases and readers, and used to protect their identities in statistical analysis and in reporting of results.

Statistician not blinded. Because the reader data on lesion locations only includes Slice for DBT, the statistician will not be blinded to reading condition.

General conventions: Descriptive summaries. Baseline descriptive summaries will include the distribution of demographic characteristics and clinical characteristics, including characteristics specific to malignant and, if appropriate, benign lesions. We also will provide summaries across readers of the per-subject number of findings, BI-RADS scores, POM scores, and per-subject recall scores, for the FFDM and DBT plus S-View readings. These may be cross-classified by, for example, presence of malignant lesions. Categorical variables (such as cancer type and breast tissue composition) generally will be summarized using frequencies and proportions or percentages, while continuous variables generally will be summarized using means and standard deviations (SDs), and/or medians and quartiles or ranges. Missing values generally will be reported as such in these descriptive summaries.

General conventions: Statistical inferences. Uncertainty in estimates of diagnostic accuracy will be quantified through confidence intervals (CIs). Unless otherwise noted, statistical inference procedures (hypothesis tests, CIs) are two-sided with significance level alpha = 0.05 and corresponding confidence level 0.95. Statistical inferences for proportions (for example, sensitivity and specificity) may use the binomial distribution or other exact methods rather than normal approximations, for example, when sample sizes are small and/or when proportions are close to zero or one. Results will be presented by reader using reader numbers to mask reader identities, and averaged across readers.

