  - Table of readers' estimates for FFDM, DBT plus S-View, and the pairwise differences between them.
  - Average across readers of within-modality estimates and between-modalities differences in between them.
  - Two-sided 95% CIs to quantify uncertainty in the within-modality estimates and the between-modalities difference.
  - Corresponding rotated forest plots and/or stacked bar charts (optional).

- *Performance metrics in important subgroups.*
  - *AUC only:* Graphs of the readers' non-parametric (trapezoidal) ROC curves based on per-subject POM scores requiring correct lesion localization for each review condition (FFDM read, DBT plus S-View read).
  - Table of readers' estimates for FFDM, DBT plus S-View, and the pairwise differences between them.
  - Average across readers of within-modality estimates and between-modalities differences in estimates.
  - Two-sided 95% CIs to quantify uncertainty in the within-modality estimates and the between-modalities difference.
  - *AUC only:* Corresponding rotated forest plots and/or stacked bar charts (optional).
- *Adverse events.* None are expected; any that are reported to BCL will be described.
- *Sample size.*
  - Magnitude and direction of difference between average AUC for DBT plus S-View and average AUC for FFDM.
  - Estimates of variance components and correlations that influence sample sizes and case mix for the pivotal reader study:  $\hat{\sigma}_{ab}^2$  for interaction of reader and modality (DBT plus S-View or FFDM),  $\hat{\sigma}_w^2$  for within-reader variance,  $\hat{\sigma}_c^2$  for variance because cases are a sample,  $\hat{r}_1$  for the correlation between AUCs from the same reader between modalities,  $\hat{r}_2$  for the correlation between AUCs from different readers in the same modality, and  $\hat{r}_3$  for the correlation between AUCs from different readers between modalities.

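### SAP 4.10 multiplies the pilot's r2 − r3 by (J − 1) without a floor or a reported interval, so a negative estimate would understate the pivotal variance

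*SAP*

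**What the plan says.** SAP 4.10 projects the pivotal variance as

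`var(A2 − A1) = (2/J){σ²_ab + σ²_w + σ²_c[1 − r1 + (J − 1)(r2 − r3)]}`

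and states: "We will use data from this pilot study to estimate the variance components and correlations in" this expression. The Modeling Framework defines r2 through the covariance "for two AUCs from different readers in the same modality, and" r3 through the covariance for different readers in different modalities. σ²_c comes from a closed-form binormal approximation, so that case numbers can be changed.

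One conservative rule is given: σ²_ab is replaced by σ²_b × (1 − r_b) "when the unbiased estimate from ANOVA is negative". No rule covers r2 < r3. SAP 5 lists "Estimates of variance components and correlations that influence sample sizes and case mix for the pivotal reader study", with no interval, bound or sensitivity range. The 95% CIs in SAP 4.6 and 5 apply to performance measures and their differences, not to these planning parameters.

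**The concern.** Supplying these parameters is the pilot's stated purpose (Protocol 7.1, SAP 1). The SAP already accepts that one pilot component can come out implausibly low and needs a rule. It gives none for the term that carries the (J − 1) multiplier.

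As J grows, every other part of the variance shrinks as 1/J, while this part tends to 2σ²_c(r2 − r3). It is the part that extra readers cannot remove. A pilot value near zero tells the planner that readers can stand in for cases. A negative value gives a negative variance once J is large enough, so it is not admissible for a population of readers. An under-powered pivotal, or a poor balance of readers and cases, could follow.

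**Working it through.** **Inputs from the documents.** Pilot readers: "six (6) board-certified radiologists" (SAP 1). Cases: "The sample includes 18 cancer cases and 82 non-cancer cases comprised of 17 benign cases, 19 recall cases, and 46 normal cases" (SAP 2.1). Tests are "two-sided with significance level alpha = 0.05" (SAP 4). Each case is read once per modality. The documents give no pivotal J, case number, power target, r1, r2, r3 or variance component, so there is no planned figure to reproduce. All such values below are assumptions.

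**1. The formula is right.** Under the SAP's model, averaging over J readers gives
- error variance within a modality: `(1/J)[σ²_c + σ²_w + (J − 1)r2σ²_c]`
- error covariance between modalities: `(1/J)[r1σ²_c + (J − 1)r3σ²_c]`

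Twice the first minus twice the second, plus `2σ²_ab/J`, is the SAP's expression.

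**2. Sensitivity to r2 − r3.** Assume σ²_c = 1, σ²_w = 0, r1 = 0.5, σ²_ab = 0.25 and true r2 − r3 = 0.05. The braces then equal 0.75 + (J − 1)(r2 − r3). The true value is 1.00 at J = 6, 1.30 at J = 12 and 1.60 at J = 18. Actual power of a study planned at 80% is `Φ(2.80 × √(planned/true) − 1.96)`.

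| Pilot r2 − r3 | J = 6: ratio, power | J = 12: ratio, power | J = 18: ratio, power |
|---|---|---|---|
| 0.02 | 0.85, 0.73 | 0.75, 0.68 | 0.68, 0.64 |
| 0 | 0.75, 0.68 | 0.58, 0.57 | 0.47, 0.48 |
| −0.02 | 0.65, 0.62 | 0.41, 0.43 | 0.26, 0.29 |

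For example, at J = 12 a pilot value of −0.02 gives 0.75 − 0.22 = 0.53, and 0.53/1.30 = 0.41. At J = 18 a value of −0.05 gives 0.75 − 0.85 = −0.10, a negative variance. Over r1 = 0.4 to 0.6 and σ²_ab = 0 to 0.5, a pilot value of 0 gives ratios of 0.62–0.81 (J = 6), 0.42–0.67 (J = 12) and 0.32–0.56 (J = 18).

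**3. How noisy the pilot estimate is.** Three simulations of the 18/82-case, 6-reader pilot under differing assumed inputs:

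| True r2 − r3 | Share of pilots with r2 < r3 |
|---|---|
| 0.018 / 0.044 / 0.089 | 36% / 15% / 3% |
| 0.02 / 0.05 / 0.10 | 33% / 11% / 2% |
| 0.02 / 0.06 / 0.11 | 26% / 6% / 1% |

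In the first row (2,000 pilots, AUC about 0.85) the SD of the estimate is 0.039, 0.044 and 0.059. In the third, 26% below zero at a mean of 0.02 implies, if roughly normal, an SD near 0.02/0.64 = 0.03.

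**4. Effect with the SAP's σ²_ab fallback applied.** In the first simulation the planned variance is more than 25% too low in 12–15% of pilots at J = 6, about 24% at J = 12 and 28–31% at J = 18. Two simulations that also removed or reduced the noise in σ²_c, with the effect size treated as known, give the share of pilots leading to power below 60%:
- σ²_c fixed at its true mean: 14–17% at J = 15 and 4–5% at J = 6
- σ²_c from an AUC-based closed form: 19–22% at J = 15, 14–15% at J = 10 and 7–10% at J = 6

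**5. What a floor does.** In the run with σ²_c fixed, flooring at zero cut the 17% at J = 15 to 6% when the true difference was about 0.02, and changed almost nothing at larger true differences. In the first simulation at J = 12, the share more than 25% too low fell from 24% to 11% at a true 0.018, and from 24% to 22% at 0.044.

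**6. Link to σ²_ab.** Since `E[MS(TR)] = σ²_ab + σ²_w + σ²_c(1 − r1 − r2 + r3)`, where MS(TR) is the reader-by-modality mean square, a low r2 − r3 also lowers the ANOVA estimate of σ²_ab. Where that estimate stays positive, the fallback does not act and the two errors add.

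**The case against.** The strongest reply is that SAP 4.10 obtains parameters and does not size anything. Sizing belongs to FMSU2017-002B, which was not supplied and may contain safeguards. SAP 5 reports r2 and r3 separately, so a negative difference would be seen. These points limit the consequence. They do not remove the gap, because SAP 4.10 already sets one conservative planning rule and leaves this term without one.

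Four stronger readings are tempting, and the documents do not support them:
- *The projection is biased downward.* The error runs both ways. In the first simulation the median planned variance, with the fallback, was 1.02 to 1.14 times the true one.
- *About 24–30% of pilots lead to power below 60%.* That range comes from a calculation at J = 15 that omits σ²_ab with its fallback and the closed-form σ²_c, both of which are in SAP 4.10. J = 15 is itself an assumption.
- *This term dominates the planning uncertainty.* The AUC difference is also taken from the pilot, with a simulated SE of 0.022–0.028. If the 0.05 margin of SAP 4.6.1 carried over and the true difference were zero, the 10th–90th percentile distance to the margin would run from 0.015–0.023 to 0.078–0.086. The required variance would then vary by (0.078/0.023)² ≈ 11 to (0.086/0.015)² ≈ 33-fold. The square bracket in the formula varies about 1.97/0.42 = 4.7-fold at J = 15 with a true difference of about 0.05.
- *A floor solves the problem.* It helps mainly when the true difference is small, so an interval is needed as well.

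**Conclusion.** The concern holds as a gap in the planning rule. The formula is correct, but SAP 4.10 would carry a negative r2 − r3 into it as it stands, and SAP 5 gives the planner no measure of its error. The under-powering rates of 14–22% at J = 15 and 4–10% at J = 6 rest on assumed reader correlations, AUCs of about 0.85–0.87, an assumed pivotal J and a known effect size. The textual gap does not depend on those assumptions; its size does, and it grows with J. Because the design has one read per modality ("When the readers review the case sample only once in each modality", σ²_ab cannot be separated from the error variance), the pilot itself cannot settle these components precisely.

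**What to change.** In SAP 4.10, beside the σ²_ab rule, state that r2 − r3 is set to max(0, estimate) in the projected variance, and also in the ANOVA estimate of σ²_ab that uses it.

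In SAP 5, add a case-bootstrap interval, resampling within cancer and non-cancer cases, for r2 − r3 and for the projected variance at each candidate J, next to the point values. The pivotal design can then be checked at an upper value. The interval covers case sampling only, since the six readers are not resampled, and the report should say so.

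The cost is a few lines of text and code, and a slightly larger planned variance when the estimate is negative. Sizing on a fixed upper percentile, such as the 80th, is optional. In simulation it raised the median planned variance to about 17–25% above the true value, so it trades a larger pivotal for a lower risk of under-powering.

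### The fallback for the reader-by-modality variance in SAP 4.10 is called conservative, but it can be zero, negative or below the true component

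*SAP*

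**What the plan says.** SAP 4.10 models each reader's AUC with two separate random terms. The term b_j "is a random effect for reader with expectation 0 and variance" σ²_b. The term (ab)_ij "is a random effect for the interaction of modality and reader with expectation 0 and variance" σ²_ab. The SAP defines r_b as "the correlation between the set of AUCs in the two (2) modalities", and A_ij as an estimated AUC, so read literally r_b is the correlation of the observed AUCs.

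The variance of the AUC difference for the pivotal study is (2/J){σ²_ab + σ²_w + σ²_c[1 − r1 + (J − 1)(r2 − r3)]}. On the first component the SAP says: "To be conservative, the component" σ²_ab is taken as σ²_b × (1 − r_b) "when the unbiased estimate from ANOVA is negative".

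The SAP gives no lower limit for this product and no formula for the estimate of σ²_b. It does not say whether r_b is corrected for error. It does note the limit of the data: "When the readers review the case sample only once in each modality", the interaction and the error term cannot be told apart. The pilot has "six (6) board-certified radiologists with a range of experience". On cases, SAP 2.1 states: "The sample includes 18 cancer cases and 82 non-cancer cases".

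**The concern.** The rule exists to repair a negative variance estimate, yet it multiplies by another moment estimate that can also be negative with six readers. If that happens, the repair fails and the planning formula receives a negative component. Even when the product is positive, nothing in the model makes it at least as large as σ²_ab, so the label is not earned.

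This matters because the pilot's stated purpose is to plan and power the pivotal study. In the planning formula σ²_ab is divided only by the number of readers; adding cases does not reduce it. A value that is too low would give a study with too few readers.

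**Working it through.** **Inputs.** From the SAP: the model, the variance formula, the fallback, J = 6 readers, 18 cancer and 82 non-cancer cases. The documents give no variance components, power or pivotal sample size, so there is no figure of the plan to reproduce. All component values below are assumptions.

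**Step 1: the variance formula.** With test values J = 6, σ²_ab = 0.0004, σ²_w = 0.0003, σ²_c = 0.002, r1 = 0.5, r2 = 0.45, r3 = 0.35, the formula gives (2/6){0.0007 + 0.002[0.5 + 5 × 0.10]} = 0.0009. The full covariance matrix of the model gives the same. The formula is right; only the fallback is in question.

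**Step 2: the sign of the fallback.** Let s11 and s22 be the sample variances of the six AUCs in each modality, s12 their covariance, S = (s11 + s22)/2, and r_b = s12/√(s11·s22). The moment estimates under the SAP model (my choice of estimator, as the SAP prints none) are:

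- σ²_b: s12 − (r1 − r3)σ²_c
- σ²_ab: S − s12 − σ²_w − σ²_c(1 − r1 − r2 + r3)

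Since 1 − r_b is never negative, the fallback takes the sign of the estimate of σ²_b.

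Example, assuming σ²_c = 0.003, σ²_w = 0.0005, r1/r2/r3 = 0.5/0.45/0.38. FFDM AUCs: 0.84, 0.86, 0.85, 0.88, 0.83, 0.86. DBT plus S-View AUCs: 0.87, 0.86, 0.88, 0.88, 0.86, 0.87.

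- s11 = 0.000307, s22 = 0.000080, s12 = 0.000080, S = 0.000193, r_b = 0.51
- σ²_ab estimate: 0.000193 − 0.000080 − 0.0005 − 0.003 × 0.43 = −0.00168, so the rule fires
- σ²_b estimate: 0.000080 − 0.12 × 0.003 = −0.00028
- Fallback: −0.00028 × 0.49 = −0.00014
- S(1 − r_b): 0.000193 × 0.49 = +0.00009

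**Step 3: the direction.** I simulated 200,000 six-reader pilots per setting with the same error values, treated as known, and the observed r_b. The pivotal study is assumed to have 12 readers and four times the cases. Its error term is then 0.0005 + 0.00075(0.5 + 11 × 0.07) = 0.00145. The ratio columns are (mean value when the rule fires + 0.00145)/(true σ²_ab + 0.00145).

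| True σ²_b | True σ²_ab | Rule fires | Fallback ≤ 0 when fired | Fallback below truth when fired | Mean fallback | Ratio, SAP rule | Ratio, S(1 − r_b) |
|---|---|---|---|---|---|---|---|
| 0 | 0 | 58% | 38% | 38% | −0.000008 | 0.99 | 1.7 |
| 0 | 0.0003 | 49% | 33% | 72% | 0.000045 | 0.85 | 1.4 |
| 0 | 0.001 | 33% | 25% | 99.7% | 0.000153 | 0.65 | 1.0 |
| 0.001 | 0 | 58% | 15% | 15% | 0.000272 | 1.19 | 1.6 |
| 0.001 | 0.0003 | 49% | 14% | 46% | 0.000302 | 1.00 | 1.4 |
| 0.001 | 0.001 | 33% | 11% | 98% | 0.000366 | 0.74 | 1.0 |
| 0.002 | 0 | 58% | 7% | 7% | 0.000410 | 1.28 | 1.6 |
| 0.002 | 0.0003 | 49% | 7% | 32% | 0.000434 | 1.08 | 1.4 |
| 0.002 | 0.001 | 33% | 6% | 94% | 0.000482 | 0.79 | 1.0 |

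A separate run over 36 assumed settings of the same model agrees in pattern. The rule fired in 14% to 59% of pilots and then returned zero or less in 1% to 28%. The median planned pivotal variance ran from 0.44 to 1.43 times the truth.

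**Step 4: what S(1 − r_b) is.** It cannot be negative. If r1 ≥ r3 it is also never below the SAP's product, because the σ²_b estimate ≤ s12 ≤ √(s11·s22) ≤ S. When s11 = s22 it equals the reader-by-modality mean square, S − s12. That mean square has expectation σ²_ab + σ²_w + σ²_c(1 − r1 − r2 + r3), so it carries error that the planning formula adds again. Nor is it a strict ceiling. The rule fires only when the mean square is below the error part, here 0.0005 + 0.003 × 0.43 = 0.00179, so a true component well above that would still be missed.

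**The case against.** The strongest defence is that the rule is conservative against the natural alternative. When the σ²_b estimate is positive and r_b is below 1, the product exceeds both the negative estimate it replaces and truncation at zero. That stands, but it does not cover the cases where the σ²_b estimate is zero or negative.

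A reader might also infer that the rule always understates. If r_b were the correlation of the readers' true AUCs, it would equal σ²_b/(σ²_b + σ²_ab). The product would then be r_b × σ²_ab, for example 60% of the component at r_b = 0.6. The documents do not support that reading, because the SAP defines r_b on estimated AUCs. Then 1 − r_b also carries case and reading error, which pushes the product up, and the table shows overstatement as well as understatement. A specific power loss does not follow either. Some assumed settings give 65% to 75% true power where 80% was planned, but the documents supply no components that would select those settings.

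Perhaps σ²_b in the product was meant as the total between-reader variance. Then one symbol has two meanings in one section, and the sentence still needs correcting. An error-corrected total would not help: it adds the negative σ²_ab estimate to the σ²_b estimate (in the example, −0.00028 − 0.00168 = −0.00196). Only the observed variance S is safe from this.

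Finally, S(1 − r_b) should not simply replace the estimate, since it counts error twice. That objection stands and shapes the fix.

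**Conclusion.** The point holds in this form: the fallback in SAP 4.10 is not guaranteed to be conservative. As written it can be zero or negative, and it can fall below the true σ²_ab. The sign result needs only the SAP's definitions and the usual moment estimate of σ²_b.

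The direction of the error is not fixed. With the observed r_b, the rule tends to overstate when the true σ²_ab is near zero, provided readers do differ, and to understate when it is larger. The sizes in the table rest on assumed components and illustrate the range; they do not predict this trial. A general claim that the pivotal variance is understated goes further than the documents allow.

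The consequence is confined to planning the pivotal study. The pilot's AUC estimates, confidence intervals and endpoints do not depend on this sentence.

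**What to change.** Revise the fallback sentence in SAP 4.10 to say:

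- r_b is the observed between-modality correlation of the six readers' AUCs.
- The value used for σ²_ab is never below zero.
- When the unbiased estimate is negative, the conservative upper planning value is S(1 − r_b), with S the average over the two modalities of the sample variance of the six AUCs. The product with the main-effect σ²_b is dropped, because it does not guarantee conservatism.
- This upper value includes case and reading error that the variance formula adds again, so it is a planning value and not an estimate of σ²_ab.
- The pivotal variance is reported over σ²_ab from 0 to S(1 − r_b).

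SAP section 5 lists the components to be reported but not σ²_b or r_b. Adding S, r_b and whether the rule fired would let a reader trace the planning value.

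The cost is a few sentences, with no new data and no change to the readings or the primary analysis. The downside is a larger upper planning variance when the rule fires. It may be well above the truth if σ²_ab is small: about 1.6 to 1.7 times in the assumed settings with σ²_ab = 0. Reporting the range shows the sponsor how much of the pivotal sample size rests on this one uncertain component.
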